6.6. GENERAL ASPECTS FOR STATISTICAL ANALYSIS

6.6.1. General Methods

All statistical analyses will be performed using SAS statistical software (Version 9.4 or later).

Part 1 summaries will be presented by treatment group (Placebo, ZX008 0.2 mg/kg/day ZX008 0.8 mg/kg/day).

Continuous data will be summarized using descriptive statistics including means, standard deviations, medians, lower and upper quartiles, minimum and maximum values. Categorical variables will be summarized with frequencies and percentages. Confidence intervals will be calculated for key parameters or estimates as warranted.

Two-sided statistical significance testing (α = 0.05) comparing each active treatment to placebo will be performed for the primary and secondary endpoints as described below, unless otherwise noted.

All relevant collected subject data will be included in listings. All subjects entered into the database will be included in data listings.

Unless otherwise specified in the subsequent sections, in the event of multiple assessments at a given planned time point, the latest collected value will be used for the summarization.

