6.6.2. Definitions

First Dose Date: First Dose Date of Investigational Drug: If the first diary date on the day after randomization indicates that investigational drug was taken on this day, then the first dose date will be the date after randomization (Study Day 1). In all other situations where it is known that the subject took at least one dose of medication, the first dose date will be assumed to be 1 day after the date of randomization.

Study Day: Study day will be calculated relative to the First Dose Date in the Titration Period. For any date on or after the date of first dose, study day will be calculated as assessment date - first dose date + 1. For any date prior to the date of first dose, study day will be calculated as assessment date - first dose date. There will be no Study Day 0.

Baseline Value: For non-seizure frequency assessments, the Part 1 baseline value will be the last non-missing assessment collected on or prior to the first date of dosing in Part 1. Unscheduled assessments prior to First Dose Date will be considered for selection of the baseline value. Baseline values for seizure frequency endpoints will be

Event Start and End Dates

Inssing start and end date will be imputed conservatively, i.e. missing values will be imputed in such a way that the duration of the AE is considered with the longest possible duration and such that, whenever the AE may potentially start after first date of study medication, the AE will be handled as a treatment-emergent adverse event (TEAE).

The missing Start date and End date of an AE will be imputed for the calculating treatment emergent status and assigning events of lefinitions given in the following table.

Adverse event | Partial | Missing | Mi

	Adverse event
Partial /Missing Start date	Missing day - If Adverse event day is missing but month and year is present then Impute the 1st of the month unless month is same as month of first dose of study drug in Part 1 then impute first dose date in Part 1. Missing day and month - If adverse event day and month are both missing but year is present then impute 1st January unless year is the same as first dose date in Part 1 then impute first dose date in Part 1. Completely missing - impute first dose date in Part 1 unless the end date suggests it could have started prior to this in which case impute

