6.7. VISIT WINDOWS

The following rules will be used to window data into treatment periods for by treatment period tabulations. For all by-visit tabulations, the nominal visit as recorded on the electronic Case Report Form (eCRF) will be used.

The following are the definitions for associating dates with the treatment periods of Part 1.

Baseline Period	The Baseline Treatment period will be the 28 days immediately prior to the date of the Study Day 1.
Double Blind	The Double-Blind Treatment Period start date is the date of
Treatment Period	first full daily dose (i.e. Study Day 1). The Double-Blind
Sell Call	Treatment Period end date is the last date the subject was on study treatment in Part 1.
Chy, Oblig	The Double-Blind Treatment Period consists of 16 weeks from first treatment start date, which includes 2 weeks of
S. S.	Titration period, 12 weeks of Maintenance period and 2 weeks of Taper/Transition period. The end date for efficacy
	analyses is the last day of Maintenance treatment, or Visit 12; the end date for safety analyses is the last day of

version 2.0	Syneos Health #1009529	7A
	Taper/Transition, which would be considered the date at Visit 15.	ation
	For subjects who discontinue early from the study, the double-blind treatment period end date for efficacy analyses will be the date at the early termination visit (Visit 12); the end date for safety analyses would be the date of Visit 13. If a taper is not conducted, the end date for both analyses would be Visit 12.	alithorization ereof.
Titration Period	The Titration Period begins on the first full day of treatment (Study Day 1) and extends through Visit 6 (when the subject has reached their randomization dose). The Titration Period applies to all subjects including placebo recipients. If a subject withdraws from the study prior to treatment in the maintenance period, all safety assessments and events up to and including the date of study withdrawal will be tabulated in the titration period.	ere .
Maintenance Period	The Maintenance Period covers the 12 weeks following the end of the titration period. It begins on the date of Visit 6 + 1 day and extends through the end of study/early termination visit (Visit 12).	
Titration + Maintenance Period (T+M)	The T+M period combines the Titration and Maintenance periods, beginning on the date of first treatment (Study Day 1) and extending through the end of study/end of treatment visit (Visit 12).	

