9.1. EXTENT OF EXPOSURE

Part 1 treatment exposure data will be summed.

Duration of total exposure.

Duration of total exposure during Part 1 (i.e., time on treatment (in days)) will be calculated per subject as the number of days with IMP intake during the trial and will be summarized using n, mean, standard error, median, minimum, Q_1 , Q_3 and maximum.

This will be calculated for non-placebo subjects as:

Date of last IMP intake in Part 1 - Date of first full daily IMP intake in Part 1 + 1 Time on treatment will be summarized by the Part 1 treatment group.

TREATMENT COMPLIANCE (DIARY) 9.2.

Study medication is to be administered twice daily, and self-reported compliance is recorded in the eDiary as full (both doses), partial (less than full daily dose) or missed (both doses) each day. From this, compliance will be calculated by assuming that a missed dose=0% of dose consumed, partial=50% of dose consumed, and full=100% of dose consumed. For each subject, a daily diary compliance score will be thus obtained.

A compliance will also be determined based on the actual quantity taken, determined using the weight of the dispensed drug kit and weight of the returned drug kit. The expected quantity taken will be determined using the assigned dosage in mg/kg/day and the number of days they were assigned at that dosage. If a kit was not returned, the compliance for the period will be missing.

For Part 1, compliance will be summarized for the SAF and mITT populations over the course of T+M period and M period only per recorded visit dates, reported by treatment group.

9.3. **ADVERSE EVENTS**

An AE is defined as any unfavorable and unintended sign (including an abnormal, clinically significant laboratory finding), symptom, or disease temporally associated with the use of a medicinal (investigational) product, whether or not considered related to the medicinal (investigational) product. For Part 1, the period of observation for adverse events extends from the time the subject gives informed consent until the end of the titration/transition period (Visit 13 or 15).

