9.3.3. Adverse Events of Special Interest (AESI)

As per International Conference on Harmonisation (ICH) guidance (E2F Development Safety Update Report [2011]), the sponsor has identified the following AESIs for the ZX008 in the table below-

Table 7 - Adverse Events of Special Interest:

Metabolic/Endocrine
1.Elevated prolactin level ≥2x above the upper limit of normal (ULN)
2. Hypoglycemia - <3.0 mmol/l or 54 mg/dl, whether that level is associated with
symptoms or not
X Y , O
Neuropsychiatric
1. Suicidal thoughts, ideation or gestures

Standardized MedDRA Queries (SMQs) will be employed as applicable to identify each AESI category or manually assigned through review. For Part 1 AEs, this will be completed and documented prior to study unblinding.

For Part 1, adverse events of special interest will be summarized by treatment group and by system organ class and preferred term.

All AESIs will be listed separately.

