9.10. LABORATORY PARAMETERS

Laboratory safety parameters will be analyzed by a central laboratory using standard validated methods.

All laboratory safety data will be collected as per the schedule of assessments given in Table 4.

The following continuous laboratory parameters will be analyzed:

- Hematology: hemoglobin, hematocrit, erythrocytes, erythrocyte mean corpuscular volume, leukocytes, neutrophils, lymphocytes, monocytes, eosinophils, basophils and platelets
- Blood Biochemistry: albumin (ALB), alkaline phosphatase (AP), alanine aminotransferase (ALT; SGPT), aspartate aminotransferase (AST; SGOT), blood urea nitrogen (BUN), calcium (Ca), carbon dioxide (CO2), chloride (Cl), creatinine, creatine kinase, gamma-glutamyl transferase (GGT), globulin, glucose, lactate dehydrogenase (LDH), phosphorus, potassium (K), sodium (Na) thyroid function, thyroid stimulating hormone (TSH), total bilirubin, direct bilirubin, total cholesterol, total protein, triglycerides, uric acid.
- Tests of growth and precocious puberty: Growth hormone (GH), insulin-like growth factor-1 (IGF-1, low sensitivity), prolactin, Luteinizing Hormone (LH), Follicle Stimulating Hormone (FSH), testosterone, estradiol
- Coagulation: Prothrombin time (PT), International normalized ratio (INR), activated partial thromboplastin time (PTT)
- Whole blood cannabidiol
- Urinalysis: analysis for pH, glucose, ketones, nitrite, protein, bilirubin, urobilinogen, leukocyte esterase, and occult blood. Microscopic analysis will be performed for blood, all cell types, and casts.
- Pregnancy test: Urine or serum pregnancy testing will be performed in female subjects of childbearing potential.
- Urine or serum THC panel

Observed continuous laboratory data will be descriptively summarized by type of laboratory test/parameter change from baseline.

Categorical laboratory parameters will be summarized by presenting the number and % of subjects by visit and by treatment arm.

For each laboratory parameter, shift tables will be created comparing the baseline status with the status at each post-baseline visit. Status will be classified as:

- below lower limit of normal and clinically significant
- below lower limit of normal,
- within normal limits,
- above upper limit of normal,
- above upper limit of normal and clinically significant.

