Listings of the most extreme values for a subject recorded in Part 1 and Part 2 will be created for each parameter. These will show the lowest recorded value and the highest recorded value noted for the subject. A listing of subjects with markedly abnormal laboratory results will be provided, and additional explorations of the data may be conducted as warranted.

Additionally, summaries of abnormal lab results by parameter will be provided to investigate changes in platelet count and prolactin in detail. The summaries include:

- Subjects with decrease (≥25% from baseline) in Platelets count with normal platelet count at baseline
- Subjects with decrease (≥25% from baseline) in Platelets count relative to baseline (whether normal or abnormal) platelet count
- Subjects with decrease (≥25% from baseline) in Platelets count with normal platelet count at baseline, by valproate use
- Subjects with decrease (≥25% from baseline) in Platelets count with normal platelet count at baseline, by presence/absence of infection event prior to 7 days of the lab assessment
- Subjects with increase (≥25% from baseline) in prolactin with normal baseline
- Subjects with increase (≥25% from baseline) in prolactin with normal baseline, and had seizure event within 48 hours prior to prolactin

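### Laboratory status shifts are counted by visit only, on the latest value at that visit; adding by-arm shifts to the lowest and highest on-treatment values is a cheap, low-severity improvement

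*SAP*

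**What the plan says.** Three provisions of the SAP act together.

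- Section 6.6.1 (General Methods), as a default that later sections may override: "in the event of multiple assessments at a given planned time point, the latest collected value will be used for the summarization".
- Section 6.7 (Visit Windows), for by-visit tables: "the nominal visit as recorded on the electronic Case Report Form (eCRF) will be used".
- Section 9.10 (Laboratory Parameters), for each parameter: "shift tables will be created comparing the baseline status with the status at each post-baseline visit". The status categories run from low and clinically significant up to "above upper limit of normal and clinically significant".

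Section 9.10 also asks for listings of each subject's lowest and highest recorded value. It adds: "A listing of subjects with markedly abnormal laboratory results will be provided". Platelets (fall of at least 25% from baseline) and prolactin (rise of at least 25%) get dedicated subject counts.

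Unscheduled results are addressed only before treatment, in section 6.6.2: "Unscheduled assessments prior to First Dose Date will be considered for selection of the baseline value".

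Outside the laboratory section, the AE definition in section 9.3 covers "any unfavorable and unintended sign (including an abnormal, clinically significant laboratory finding". For the Part 1 AESIs, section 9.3.3 says that "adverse events of special interest will be summarized by treatment group and by system organ class and preferred term".

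**The concern.** A latest-value rule is sensible for by-visit means, where one value per subject per visit is needed. It suits counts of abnormality less well. Abnormal results are the ones most likely to be repeated, so the rule tends to replace an abnormal value with a later one. Where the by-visit shift is the only laboratory status table by arm, a transient on-treatment abnormality can drop out of the randomised comparison even though the sample was taken and the value is stored.

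Elsewhere the plan does count at any time on treatment: weight and BMI changes (section 9.6), C-SSRS responses (section 9.11), and pulmonary artery systolic pressure (cardiovascular SAP, section 2.3.1.2). Laboratory status has no such count. What is at stake is the completeness of the descriptive laboratory safety tables. No efficacy result is involved.

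**Working it through.** The plan gives no figure to reproduce here. The check is to follow one result through the rules and look for an override.

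**Tracing one case.** Take Visit 8 as an illustration, with a parameter that was normal at baseline.

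1. The Visit 8 sample is abnormal. A repeat, also recorded as Visit 8, is normal.
2. Section 6.7 places both values at Visit 8 by label.
3. Section 6.6.1 keeps the later one.
4. The section 9.10 shift cell is normal to normal at Visit 8.
5. If no other visit is abnormal, the subject is in no abnormal cell of the shift table.

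**Looking for an override in section 9.10.**

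| Provision | Does it put the value in a by-arm count? |
|---|---|
| Extreme-value and markedly abnormal listings | No. They keep the value, subject by subject. |
| Platelet counts | Unclear. The index titles refer to Part 1 without naming a visit, but the text does not say whether repeat or unscheduled values count. |
| Prolactin counts | Unclear in the text. The index titles are by visit week. |
| Worst-value or any-time status shift | None is specified. |

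The SAP addendum does not change this. Its described modifications do not touch laboratory handling, and its output list marks no change to the laboratory summary or shift tables. The conclusion rests on the text of section 9.10. It does not rest on the table index, because the addendum shows that some outputs were in the shells but missing from the index.

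**Changing the label.** If the repeat is entered as unscheduled, step 3 has nothing to replace. The abnormal value stays as the Visit 8 status and nothing is lost. The SAP does not say how laboratory repeats are labelled. An abnormality seen only at an unscheduled post-baseline draw has no assigned cell in a by-visit table.

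**Size.** The share of abnormal visit values turned into normal ones is

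P(repeated under the same label) × P(repeat is normal, given that it was repeated).

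Neither factor is in the document. The product can be anything from 0 to 1, and it is 0 if repeats are labelled unscheduled. For scale only, one subject is worth 100/79 = 1.27 percentage points of an arm at the planned 79 per group. At 250/3 = 83.3 per group it is 1.20 points, and at 63 it is 1.59. These are weights of a single subject and do not estimate any effect of the rule.

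**The case against.** The case against is substantial, and most of it stands as a limit on the consequence.

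- **The mechanism depends on labelling that the SAP does not state.** The plan treats unscheduled assessments as a separate category before first dose, and repeats may well be handled that way after baseline. This stands, and the loss may be nil.
- **The most serious results have another route.** A clinically significant laboratory finding is an AE by definition, so once reported it enters the by-arm AE tables whatever the repeat shows. Prolactin at or above twice the upper limit and glucose below 3.0 mmol/l are AESIs. This also stands. What is left is values not reported as either, a less consequential group.
- **Extremes are kept.** Section 9.10 lists each subject's lowest and highest values, and listings are sorted by treatment group. This stands in part: a listing preserves the value but gives no rate by arm. The extreme-value listing also covers Parts 1 and 2, and the text does not say whether each part gets its own extreme.
- **Routine vital signs follow a similar pattern**, with by-visit summaries plus a subject-level display of the most abnormal value. True, but this does not argue against a worst-value shift table.

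Two stronger readings might be inferred. One is that a shift table and an AE table that differ on the same result contradict each other. They do not: the first shows status at a visit and the second counts events over a period. The other is that the rule hides abnormal results or favours the active arms. The values remain in the listings, and the rule is neutral between arms as written.

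**Conclusion.** The point holds as a low-severity improvement. On the text, an abnormal on-treatment laboratory value followed by a normal repeat under the same visit label is tabulated as normal, and no by-arm worst-value laboratory table is specified. A transient abnormality not reported as an AE or AESI may therefore be visible only in subject listings.

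This rests on two conditions that the SAP leaves open: that some repeats share the original visit label, and that the platelet and prolactin counts follow the default rule. The magnitude is unknown and may be zero. The documents do not support a claim that laboratory safety is materially understated. The missing rules for unscheduled post-baseline values, and for which values the platelet and prolactin criteria use, are gaps in detail rather than errors.

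**What to change.** Keep the latest-value rule for by-visit means, mean changes and by-visit shifts. Add to section 9.10:

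1. By-arm shift tables from baseline status to the status of the lowest, and of the highest, on-treatment value over T+M, using scheduled, repeat and unscheduled results.
2. A sentence applying the platelet (fall of at least 25%) and prolactin (rise of at least 25%) criteria to any on-treatment value.
3. A sentence saying where unscheduled post-baseline values go in by-visit tables.

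The cost is SAP wording and up to about one extra table per laboratory panel. No new data are needed. The drawback is that worst-value tables will count some spurious first samples, for example a faulty draw corrected on repeat. The by-visit tables should therefore stay alongside them, so that a reader can tell a transient finding from a sustained one.

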6.6.2. Definitions

First Dose Date: First Dose Date of Investigational Drug: If the first diary date on the day after randomization indicates that investigational drug was taken on this day, then the first dose date will be the date after randomization (Study Day 1). In all other situations where it is known that the subject took at least one dose of medication, the first dose date will be assumed to be 1 day after the date of randomization.

Study Day: Study day will be calculated relative to the First Dose Date in the Titration Period. For any date on or after the date of first dose, study day will be calculated as assessment date - first dose date + 1. For any date prior to the date of first dose, study day will be calculated as assessment date - first dose date. There will be no Study Day 0.

Baseline Value: For non-seizure frequency assessments, the Part 1 baseline value will be the last non-missing assessment collected on or prior to the first date of dosing in Part 1. Unscheduled assessments prior to First Dose Date will be considered for selection of the baseline value. Baseline values for seizure frequency endpoints will be

Event Start and End Dates

Inssing start and end date will be imputed conservatively, i.e. missing values will be imputed in such a way that the duration of the AE is considered with the longest possible duration and such that, whenever the AE may potentially start after first date of study medication, the AE will be handled as a treatment-emergent adverse event (TEAE).

The missing Start date and End date of an AE will be imputed for the calculating treatment emergent status and assigning events of lefinitions given in the following table.

Adverse event | Partial | Missing | Mi

	Adverse event
Partial /Missing Start date	Missing day - If Adverse event day is missing but month and year is present then Impute the 1st of the month unless month is same as month of first dose of study drug in Part 1 then impute first dose date in Part 1. Missing day and month - If adverse event day and month are both missing but year is present then impute 1st January unless year is the same as first dose date in Part 1 then impute first dose date in Part 1. Completely missing - impute first dose date in Part 1 unless the end date suggests it could have started prior to this in which case impute
	the 1st January of the same year as the end date. When imputing a start date, ensure that the new imputed date is sensible i.e., is prior to the end date of the AE.
Partial /Missing End date	Missing day - If AE end day is missing but month and year are present then Impute the last day of the month unless month is same as month of last dose of study drug then impute last dose date.
STILL SIGNI	Missing day and month - If AE has missing day and month but year is present then impute 31st December unless year is the same as first dose date then impute last dose date.
	Completely Missing - need to look at whether the AE is still ongoing before imputing a date and also when it started in relation to study drug. If the ongoing flag is missing then assume that AE is still present

(i.e. do not impute a date). If the AE has stopped and start date is
prior to first dose date then impute the 1st dose date. If the AE started
on or after the first dose date then impute the last dose date.

Data Handling for Seizure Diaries

Seizures are recorded in the Daily Seizure Diary (DSD). On each day, subjects are asked a question of whether there is a seizure to report that day. Subjects may either answer "Yes" and continue to complete more details about the seizure, or answer "No, this day has been seizure free". There will be no explicit imputation of intermittent missing data for seizure diaries. Missing seizure diary data will be handled as follows:

- If no seizures are entered in the DSD and the response to the question, is there a seizure to report that day, is "No, this day has been seizure free" then that day will have the seizure count set to 0.
- If seizures are entered in the DSD and the response to the question, is there a seizure to report that day, is "No this day has been seizure free" the seizures entered in the DSD will supersede the seizure freedom affirmation.
- If no seizures are entered in the DSD and there is no response to the question, is there a seizure to report that day, that day will be considered to have missing diary data.
- If no seizures are entered in the DSD and it is indicated that there were seizures that day, that day will be considered to have missing diary data.

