- c: The safety follow-up visit will be conducted for subjects who either terminate early from Part 1, or who complete Part 1 but do not enter Part 2. Standard follow-up visits should occur 3 and 6 months after the last dose. For subjects enrolled in Germany, France and Netherlands, follow-ups will also occur 24 months after the last dose. If there are any findings at the last post-dose follow-up, a follow-up visit will be repeated every 3 months until resolved or stabilized.
- d: The Visit 8 ECHO must be performed any time between Study Day 40 and Study Day 54. The Visit 12 ECHO must be performed any time between Study Day 90 and Study Day 113; if a subject discontinues early from the study, the ECHO should be scheduled as soon as practical. If the Study Day 43 ECHO was completed ≤ 30 days prior to early termination, the Visit 12 ECHO will not be performed provided the parent/guardian agrees to bring the subject to the clinic for the cardiac follow-up visit.
- e: Females of child-bearing potential
- f: Plasma sample for pharmacokinetic assessment will be conducted prior to the dose at Visit 8 and 1, 2, and 4-6 hours after dose administration.
- g: Plasma sample for assessment of background AED(s) will be conducted prior to the dose of AED(s) at Visits 3, 8 and 12 (Visits 6 and 10 only if clinically indicated). AED plasma sample may be collected after the morning dose of AEDs are taken, if preferable, as long as the time of last dose is accurately recorded.
- h: Study drug/diary dispensed for the Transition Period for subjects entering the open-label extension and for the Taper Period for subjects exiting the study.
- i: Site personnel will review study medication dosing procedure (titration) with parent/caregiver.
- j: Study drug administration begins in the morning of Study Day 1. Study Day 1 is considered the first day of dosing, even though subjects may receive an in-clinic dose on Study Day -1. If the first dose is taken in the clinic, it will be recorded in the eCRF, but not the subject diary; the next dose on the morning of Study Day 1 will be the first entry in the subject's diary.
- k: Only adverse events related to cardiac safety will be collected at this visit.
- 1: Visit 13 may be conducted as a phone call, provided diaries and study medication are returned by this time.
- m: An abbreviated physical and/or neurological examination to be conducted as appropriate based on last exam and reported AEs.

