A treatment-emergent adverse event (TEAE) in Part 1 is defined as any AE that based on start date information occurs after the first intake of study treatment in Part 1, but not on or after the first dose of study treatment in Part 2. For subjects who participate in Part 2, the Part 1 TEAE will include events with onset up to the day prior to the date of first dosing in Part 2. A Part 1 TEAE will be further classified into the Titration Period, Maintenance Period, and Transition/Taper Period. The Titration Period will include all events with onset from the date of the Visit 6. The Maintenance period will include all events with onset from the day after Visit 6 through the date of Visit 12. The Transition/Taper period will include all events with onset starting with the day after Visit 12 through Visit 15.

For Part 1, tables will present TEAE data by assigned treatment group received in Part 1. AEs occurring after enrollment and prior to the first administration of study treatment in Part 1 are defined as non-treatment emergent AEs (non-TEAEs).

AEs are categorized as related or unrelated. If the AE is thought to be definitely, probably or possibly related to study drug then it is to be categorized as related. Possibly or definitely unrelated is categorized as unrelated. Any TEAE with missing relationship will be considered as "related."

The severity of AEs (for both nonserious and serious AEs) will be assessed by the investigator as follows:

Severity Definition of Adverse Events:

Mild - A type of AE that is usually transient and may require only minimal treatment or therapeutic intervention. The event does not generally interfere with usual activities of daily living.

Moderate - A type of AE that is usually alleviated with additional specific therapeutic intervention. The event interferes with usual activities of daily living, causing discomfort but poses no significant or permanent risk of harm to the research participant.

Severe - A type of AE that interrupts usual activities of daily living, or significantly affects clinical status, or may require intensive therapeutic intervention.

Any AE with missing severity will be imputed as "severe."

The original terms used by the investigators in the eCRFs to identify AEs will be coded using the MedDRA Version 20.1 or later.

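### First Dose Date ignores a recorded in-clinic dose on Study Day -1, so the TEAE status and period of an adverse event later that day are not settled

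*SAP*

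**What the plan says.** Section 6.6.2 defines First Dose Date in two branches. If the diary for the day after randomisation shows drug taken, the date is that day. In all other situations where a dose is known to have been taken, "the first dose date will be assumed to be 1 day after the date of randomization". Study Day is counted from this date.

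Footnote j to the Table 4 schedule says "Study Day 1 is considered the first day of dosing, even though subjects may receive an in-clinic dose on Study Day -1". It adds: "If the first dose is taken in the clinic, it will be recorded in the eCRF, but not the subject diary".

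Section 9.3 calls an AE treatment-emergent if, on its start date, it "occurs after the first intake of study treatment in Part 1". It calls an AE non-treatment-emergent if it comes after enrolment and before the first administration of study treatment. Neither sentence uses the defined term First Dose Date.

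The rules in section 6.6.2 for partial or missing AE dates do use the first dose date. Their stated aim is that, "whenever the AE may potentially start after first date of study medication", the event is handled as a TEAE.

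Section 6.7 starts both the Titration Period and the T+M period on Study Day 1. Section 9.3.1 requires the AE overview for the full Part 1 period and for each sub-period, including Titration and T+M.

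**The concern.** The rule assumes a date that the trial actually collects. Neither branch looks at the clinic dose in the eCRF, so First Dose Date is one day late for any subject whose first dose was taken in the clinic on the day of randomisation.

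Study Day 1 as the nominal first dosing day is harmless for numbering days or windowing the seizure diary. It matters for safety, where the question is whether an event came before or after exposure. An event within hours of the first dose is one a safety reviewer would want in the TEAE tables. The plan leaves its class to whichever reading the programmer adopts, and gives it no place in the period tables.

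**Working it through.** No figure in the plan needs reproducing. The check applies the plan's date rules to one case: a subject randomised on date R who takes the first dose in the clinic on R.

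**Inputs**

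- First Dose Date F (section 6.6.2): diary branch, F = R + 1; all other situations, F = R + 1. The branches agree.
- Study Day (section 6.6.2): date − F + 1 for dates on or after F; date − F for earlier dates.
- TEAE status, reading A: onset on or after F.
- TEAE status, reading B: onset after the actual first intake on R (section 9.3, literal).
- Titration and T+M (section 6.7): from Study Day 1.

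**Results**

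| AE onset | Study Day | TEAE, reading A | TEAE, reading B | In Titration and T+M by date |
|---|---|---|---|---|
| R − 1 | (R − 1) − (R + 1) = −2 | No | No | No |
| R, after the clinic dose | R − (R + 1) = −1 | No | Yes | No |
| R + 1 | (R + 1) − (R + 1) + 1 = 1 | Yes | Yes | Yes |
| R + 2 | (R + 2) − (R + 1) + 1 = 2 | Yes | Yes | Yes |

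Only the second row differs between readings. From Study Day 1 onward the choice of date changes nothing.

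**Which reading would be programmed?** Section 9.3 does not say how first intake is to be derived. First Dose Date is the only first-dose date the SAP defines, and the AE date-imputation table, which serves treatment-emergent status, uses it. Reading A is therefore a plausible implementation, though not a stated one. It would have an odd effect: an AE with a missing start day in the month of first dose is imputed to First Dose Date and handled as a TEAE, while an AE dated exactly to Study Day -1 after the dose is not.

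**Period assignment.** Under reading B the event enters the full Part 1 overview but has no place in Titration or T+M, because section 6.7 starts both on Study Day 1. The Titration sentence in section 9.3 does not resolve this: it names Visit 6 but gives no starting date.

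**Baseline.** Section 6.6.2 takes the last non-missing value on or before the first date of dosing, and admits unscheduled values before First Dose Date. With F = R + 1, a value taken on R after the clinic dose qualifies.

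**The case against.** The strongest reply is that section 9.3 governs TEAE status and rests on first intake, not on First Dose Date. Read literally, it already counts a post-dose event on Study Day -1. Where the SAP means Study Day 1 it tends to say so, referring to the first full daily dose in section 6.7 and the first full daily intake in section 9.1. This stands. A reader might infer that the plan classes events after the clinic dose as pre-treatment; the text does not say that. The misclassification is a risk of implementation, and it is confined to onsets later on the same day.

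Several further limits also stand:

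- The conservative clause in section 6.6.2 concerns AEs with missing dates. It does not govern an AE with a complete onset date, so there is no direct contradiction with it.
- The baseline exposure is narrow. Sections 9.4 and 9.6 place the Visit 3 physical examination and vital signs before the first dose. The cardiovascular SAP fixes the ECG baseline at Visit 3 (section 3.1.4) and the ECHO baseline at Screening (section 3.2.4), so neither depends on First Dose Date. Table 4 has no clinic visit on Study Day 1. What remains is an unscheduled value, or a scheduled one with no stated pre-dose rule, taken after a clinic dose.
- The events are not lost. Section 9.3.2 lists all AEs for all enrolled subjects, with separate listings for serious AEs, AEs leading to discontinuation and deaths.
- A count of affected subjects is tempting but would mislead. If 20% to 60% of about 250 randomised subjects were dosed in the clinic (an assumption; the SAP gives no share), 0.20 × 250 = 50 to 0.60 × 250 = 150 would come under the rule. Those are subjects, not events. A subject matters here only if an AE starts in the remaining hours of that day, and no rate for that is available.
- A bias in favour of the drug would require early drug reactions. The SAP gives no basis for assuming them, and section 9.3.2 plans no inferential comparison of AEs.

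The reply does not remove the late First Dose Date, the lack of any statement tying first intake to a recorded date, or the gap in the period tables.

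**Conclusion.** The point holds as an inconsistency among footnote j, section 6.6.2, section 9.3 and section 6.7. For subjects first dosed in the clinic, First Dose Date is one day late. An AE starting on Study Day -1 after that dose is then a TEAE or not depending on which anchor is programmed, and is outside Titration and T+M in both cases.

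The effect is small and cannot be quantified from the SAP. It is limited to the rest of one calendar day, to clinic-dosed subjects whose number is not given, and to events whose number is not given. The possible consequence is an under-count of early post-dose events in the TEAE tables, not their loss from the record. The conclusion assumes only that some subjects were dosed in the clinic as footnote j permits. It does not show that the safety tables are biased towards ZX008. The change is still worth making because the correct date is already collected.

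**What to change.** For safety analyses:

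1. Define the first dose date as the earlier of the in-clinic dose date in the eCRF and the first diary dose date.
2. Anchor TEAE status on it: onset after the dose, or onset on that date if the time is unknown. State in section 9.3 that first intake means this date.
3. Assign post-dose events on Study Day -1 to the Titration and T+M periods.
4. Take the baseline for non-seizure assessments as the last value before that dose.

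Keep Study Day 1 for study-day numbering and for the diary-based efficacy periods, where the convention works.

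The cost is a few lines of SAP text and one derivation from data already in the eCRF. The small downside is that a few Study Day -1 events of uncertain timing would be counted as TEAEs. That errs in the same direction as the plan's handling of missing AE dates.
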